12.1.2.1. Hypotheses

Statistical testing will be performed to determine if the de novo dyspareunia rate of treatment group is non-inferior to the control group. The null hypothesis is that the de novo dyspareunia rate in treatment group is greater than or equal to the rate in control group plus margin:

$$H_0: \pi_{treatment} - \pi_{control} \geq \Delta$$

The alternative hypothesis is:

$$H_a: \pi_{treatment} - \pi_{control} < \Delta$$

where $\pi_{treatment}$ and $\pi_{control}$ are the de novo dyspareunia rate in treatment group and control group respectively, and $\Delta > 0$ is defined as the non-inferiority margin.

Statistical testing will be performed to determine if the AE incidences (pelvic pain, infection, vaginal shortening, atypical vaginal discharge, neuromuscular problems, vaginal scarring, de novo vaginal bleeding, fistula formation and/or de novo voiding dysfunction) rate of treatment group is non-inferior to the control group. The null hypothesis is that the AE incidences rate in treatment group is greater than or equal to the rate in control group plus margin:

$$H_0: \pi_{treatment} - \pi_{control} \geq \Delta$$

The alternative hypothesis is:

$$H_a: \pi_{treatment} - \pi_{control} < \Delta$$

where $\pi_{treatment}$ and $\pi_{control}$ are the AE incidence rates in treatment group and control group respectively, and $\Delta > 0$ is defined as the non-inferiority margin.

The propensity score adjusted confidence intervals described in Section 12.2.3 (Propensity Score Methodology) will be used to summarize the mean score improvement of Quality of Life (PFIQ, PFDI, PISQ, TOMUS pain scale) of the Xenform (treatment) group compared to that of the native tissue repair (control) group.

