12.1.2.3. Statistical Methods

A comparison of data for all subjects will be included per the following statistical analyses to measure for secondary endpoints:

- Rate of adverse device or procedure related events within 6, 12, 18, 24 and 36 months
- Overall rate of adverse device or procedure related events within 6, 12, 18, 24, 36 months
- Comparison of adverse device or procedure related events between treatment groups
- Rate and severity of Xenform exposure and erosion within 6, 12, 18, 24, 36 months
- Assessment of rate of adverse device or procedure related events in subjects with reoperation for failed prolapse repair
- Assessment of rates of/times to reoperation
- Comparison of rate of adverse device or procedure related events in subjects with re-surgery in both treatment groups
- Assessment and comparison between groups of analgesic intake and pain scoring at post-operative 6 weeks, 12, 18, 24, 36 months. Pain score improvement will be analyzed with a paired t-test for each group on all patients and with the propensity score adjusted confidence intervals for the pain score differences between groups. Change in analgesic intake from baseline will be analyzed by McNemar's test for each group on all patients.
- Assessment of severe blood loss during surgical procedure
- Duration of surgery from operative report
- Assessment of re-treatment interventions (i.e. surgery, office-procedure, etc.)
- Assessment of days to discharge and return to normal activity
- Assessment of risk factors, including menopausal status, estrogen use, age smoking, diagnosis of diabetes, body mass index, concomitant procedures, surgeon training and experience

A comparison of data between baseline and 36 months for all subjects will be included per the following statistical analyses to measure for secondary endpoints:

- Quality of Life Assessments (PFIQ, PFDI, PISQ, TOMUS) at 6, 12, 18, 24, 36 months as compared to baseline: paired t-test will be used to compare mean QOL score improvement from baseline to 6, 12, 18, 24 and 36 months for each group.
- Comparison of Quality of Life Assessments improvements between treatment groups
- Assessment of Quality of Life in subjects with re-surgery after re-surgery
- Assessment of subject satisfaction at 6, 12, 18, 24, 36 months (PGI-I for Prolapse)

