Propensity score adjusted confidence intervals described in Section 12.2.3 (Propensity Score Methodology) will be used to evaluate continuous variables including QOL score improvements between two groups.

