12.2.3. Propensity Score Methodology

Analyses comparing the treatment groups will be adjusted for the propensity score. The propensity score is the probability that the subject enrolled in the mesh arm rather than the native tissue (control) arm, given the characteristics of the subject and center. The characteristics identified are as follows: age, race, body mass index, smoking, diabetes, post-menopausal, prior prolapse repair, prior hysterectomy, estrogen use, POP-Q C measurement, POP-Q Ba measurement, POP-Q Bp measurement, concomitant repair for stress urinary incontinence, and surgeon case volume. Logistic regression of both treatment arms (i.e., (transvaginal biologic mesh repair vs. native tissue repair) on these characteristics will be used to estimate the propensity score. The subjects will then be partitioned into five strata corresponding to quintiles of the propensity score. If the balance between treatment arms within the strata is deemed adequate, the treatment difference adjusted for propensity score stratum will be estimated as described in the following.

The propensity adjusted treatment difference will be based on averaging the treatment differences of the propensity score strata. For a binary outcome, the within-stratum treatment difference is $D_j = p_{T_j} - p_{C_j}$, where p_{T_j} and p_{C_j} is the proportion of treatment and control subjects, respectively, in stratum j . The variance of D_j is approximately

$$V_j = \frac{p_{T_j}(1 - p_{T_j})}{n_{T_j}} + \frac{p_{C_j}(1 - p_{C_j})}{n_{C_j}}$$

Denoting the number of subjects in stratum j by $n_j = n_{T_j} + n_{C_j}$, the treatment difference will be estimated by the (weighted) mean of the within-stratum treatment differences

$$D = \sum_j \frac{n_j}{n} D_j$$

where $n = \sum_j n_j$ is the total sample size across all strata and study arms. D is approximately normally distributed with variance

$$V = \sum_j \left(\frac{n_j}{n}\right)^2 V_j$$

from which a confidence interval for the true treatment difference will be constructed. For each continuous outcome, the confidence interval will be constructed similarly, with D and V obtained as above with the treatment difference within each stratum replaced by $D_j = \bar{X}_{T_j} - \bar{X}_{C_j}$, where \bar{X}_{T_j} and \bar{X}_{C_j} , respectively, is the mean of the treatment and control subjects, and

$$V_j = \frac{S_{T_j}^2}{n_{T_j}} + \frac{S_{C_j}^2}{n_{C_j}}$$

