12.3.5. Sub-Analysis for Sling Repair and Interventions for Recurrence

12.3.5.1. Subjects with only POP repair and those with sling and prolapse repair

A two sample t-test will be performed in pain score change from baseline to each follow-up visit within Xenform or native tissue repair group, to compare groups with and without SUI surgery. Using this method of analysis will make it less difficult to assess causality for adverse events, including pain.

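### Between-arm comparisons of PFDI-20, PFIQ-7, PISQ-12, TOMUS and EQ-5D use propensity-stratified change scores in which the outcome's own baseline value is neither a propensity variable nor a covariate

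*Combined protocol and SAP*

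**What the plan says.** All references are to the combined protocol and SAP.

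- **Between-arm QOL.** Section 12.1.2.1 says that the 12.2.3 intervals "will be used to summarize the mean score improvement of Quality of Life (PFIQ, PFDI, PISQ, TOMUS pain scale"). Section 12.1.2.3 repeats that these intervals "will be used to evaluate continuous variables including QOL score improvements between two groups".
- **Between-arm pain.** Section 12.1.2.3 analyses pain "with the propensity score adjusted confidence intervals for the pain score differences between groups".
- **EQ-5D.** Section 12.3.6 uses the same intervals.
- **Estimator.** For a continuous outcome, 12.2.3 takes the difference of arm means in each propensity quintile (each term "is the mean of the treatment and control subjects"). It averages these differences with weights n_j/n and takes the variance from the sample variances. There is no covariate term.
- **Propensity model.** The characteristics are "age, race, body mass index, smoking, diabetes, post-menopausal, prior prolapse repair, prior hysterectomy, estrogen use, POP-Q C measurement, POP-Q Ba measurement, POP-Q Bp measurement", then "concomitant repair for stress urinary incontinence, and surgeon case volume". That is 12 + 2 = 14, and none is a baseline patient-reported score.
- **Baseline data.** Section 11.4.2 and Table 11.1-1 collect PFDI-20, PFIQ-7, PISQ-12, TOMUS and EQ-5D before surgery.
- **Sling sub-analysis.** Section 12.3.5.1 states: "A two sample t-test will be performed in pain score change from baseline to each follow-up visit". It compares women with and without a sling inside each arm, and adds that this makes causality of adverse events, including pain, easier to judge.

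**The concern.** The baseline value of a score is usually among the strongest predictors of its follow-up value. Leaving it out has two consequences.

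The first is precision. A change score fixes the slope of follow-up on baseline at 1. If the true slope is lower, the interval is wider than it need be.

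The second is confounding. Treatment is not randomized. Centers are chosen by arm (8.2), each physician is limited to one arm (10.1), and some controls may come from the registry (8.1). Nothing in the design balances baseline symptom scores, and the propensity score balances them only as far as its 14 characteristics predict them. Entry also requires a bothersome bulge (9.2, criterion 4), so some regression to the mean is to be expected.

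At stake is secondary endpoint 4, together with EQ-5D. In 12.3.5.1 there is the further problem that slings are placed at the physician's discretion, and the t-test has neither propensity nor baseline adjustment.

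**Working it through.** **The plan's own figure.** The documents give no SD, margin or power for QOL or pain. The evaluable size comes from the primary effectiveness calculation in 12.1.1.2: 70% success in both arms, margin 12%, one-sided alpha 0.05, power 80%.

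n = (1.645 + 0.842)² × 2 × 0.70 × 0.30 / 0.12² ≈ 180.4, so 181 per arm. With 20% loss, 181 / 0.80 = 226.25, so 227 per arm. Both figures reproduce and neither is disputed.

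**Assumptions not in the documents.** Equal SD at baseline and follow-up; correlation r of 0.3, 0.5 or 0.7; a baseline difference of 0.2 SD between arms.

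**Formulas, in SD units.**

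- Variance of a change score: 2(1 − r).
- Variance after regression on baseline: 1 − r².
- Ratio: (1 − r²) / [2(1 − r)] = (1 + r)/2.
- 90% half-width at 181 per arm: 1.645 × √(variance × 2/181).
- Bias of the change score: if follow-up has mean a + r × baseline in both arms, improvement (baseline minus follow-up) has mean (1 − r) × baseline − a. A within-stratum baseline difference δ therefore contributes (1 − r)δ.

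| r | Variance, change | Variance, adjusted | Ratio | Half-width, change | Half-width, adjusted | Narrower by | Bias at δ = 0.2 SD |
|---|---|---|---|---|---|---|---|
| 0.3 | 1.40 | 0.91 | 0.65 | 0.205 | 0.165 | 19% | 0.14 |
| 0.5 | 1.00 | 0.75 | 0.75 | 0.173 | 0.150 | 13% | 0.10 |
| 0.7 | 0.60 | 0.51 | 0.85 | 0.134 | 0.123 | 8% | 0.06 |

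The percentage narrowing does not depend on the confidence level. If the follow-up SD is 0.8 of the baseline SD, the variance ratio is 0.50, 0.57 and 0.63 at these r, a larger saving.

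**Simulation check.** There were 600 runs per setting with 181 per arm, five strata, no true effect and a 0.2 SD baseline difference. The plan's estimator was compared with a regression on stratum, arm and baseline score.

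- *Baseline score unrelated to the propensity covariate.* The plan's estimator had bias 0.14, 0.10 and 0.06 SD at r = 0.3, 0.5 and 0.7. Coverage of the 90% interval was 71%, 76% and 84%. With the baseline score added, bias was about 0 and coverage 89% to 92%.
- *Baseline score correlated 0.3 with a propensity covariate that also differs between arms.* Bias fell to 0.07, 0.05 and 0.03 SD, with coverage 85% to 88%. Here stratification removed roughly half the problem. That fraction is particular to this setting.

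The simulated data follow the model that favors baseline adjustment. They check the arithmetic; they do not show that this model is the right one.

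**The case against.** A reader might infer that these are raw change scores with no baseline adjustment. The documents do not support that for the main comparison. It is stratified on 14 characteristics, including three POP-Q measurements and prior prolapse repair; it is used only if within-stratum balance is judged adequate; and the change score itself subtracts baseline. Only the t-test in 12.3.5.1 lacks propensity adjustment altogether.

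A reader might also infer that endpoint 4 is biased. No imbalance in baseline scores is reported, and both arms share the same entry criteria. Bias is a possibility, not a finding.

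The strongest objection is Lord's paradox. The result (1 − r)δ holds only if women with the same baseline score would have the same expected follow-up in either arm, absent a treatment effect. If the gap is instead a stable difference between the populations of different centers, the change score is unbiased and the baseline-adjusted estimate is off by (1 − r)δ. The documents cannot settle this. The objection stands as a reason to report both analyses. It does not touch the precision argument.

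Section 12.3.10 does mention ANCOVA for subject-reported outcomes. It looks for predictors within each arm and names no baseline score, so it does not fill the gap.

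Finally, the stakes are modest and the date is late. Enrollment ended in December 2016, and the 12-month interim analysis (12.3.8) may already report secondary endpoints by arm. This argues for a prompt, documented change and for retaining the planned analysis.

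**Conclusion.** The point holds as a limited one. For five outcomes, a baseline value that is already collected enters the between-arm comparison neither through the propensity score nor as a covariate.

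The loss of precision is the firmer half: 15% to 35% of the variance, or about 8% to 19% of interval width, for assumed r from 0.7 down to 0.3 with equal SDs. The bias is conditional. It needs a baseline imbalance within strata and a common regression of follow-up on baseline. At an assumed residual imbalance of 0.2 SD it is 0.06 to 0.14 SD, and it is less where the propensity covariates already capture part of the imbalance.

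The endpoints are secondary, with no stated margin or power for QOL or pain. The primary effectiveness and safety conclusions are unaffected.

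**What to change.** 1. **Section 12.2.3, continuous outcomes with a baseline value (PFDI-20, PFIQ-7, PISQ-12, TOMUS, EQ-5D).** Make the main analysis a regression of the follow-up score on arm, propensity stratum, arm-by-stratum and baseline score. Pool the stratum-specific arm differences with the existing n_j/n weights. Take the variance of that weighted contrast from the model's covariance matrix: a slope shared across strata makes the D_j correlated, so the formula V = Σ(n_j/n)²V_j no longer applies. Cross-refer from 12.1.2.1, 12.1.2.3 and 12.3.6. SSQ-8 and PGI-I have no baseline value and stay as they are.
2. **Sensitivity analysis.** Keep the planned propensity-stratified change-score analysis, and state that the two rest on different assumptions in a non-randomized study.
3. **Section 12.3.5.1.** Replace the t-test with ANCOVA on sling status plus baseline TOMUS. Qualify the sentence on causality, because sling placement is at physician discretion and baseline pain alone does not remove that confounding.
4. **Timing.** Specify this before the 36-month outcomes are analysed, and record that the 12-month interim analysis may have preceded it.

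The cost is revised SAP wording, a small amount of extra analysis, and a second estimate per outcome that may differ from the first. No new data are needed, and the propensity strata used for the primary endpoints do not change.

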12.1.2.2. Sample Size

The rate of de novo dyspareunia is anticipated to be approximately 9%.¹⁷ With type I error of 0.05 and type II error of 0.20 (power 80%), 326 subjects (163 subjects per arm) are needed to detect non-inferiority with a margin of 7.9%.

The rate of AE incidence (pelvic pain, infection, vaginal shortening, atypical vaginal discharge, neuromuscular problems, vaginal scarring, de novo vaginal bleeding, fistula formation and/or de novo voiding dysfunction) is anticipated to be approximately 12%.¹⁵⁻¹⁸ With type I error of 0.05 and type II error of 0.20 (power 80%), 330 subjects (165 subjects per arm) are needed to detect non-inferiority with a margin of 8.9%.

12.1.2.3. Statistical Methods

A comparison of data for all subjects will be included per the following statistical analyses to measure for secondary endpoints:

- Rate of adverse device or procedure related events within 6, 12, 18, 24 and 36 months
- Overall rate of adverse device or procedure related events within 6, 12, 18, 24, 36 months
- Comparison of adverse device or procedure related events between treatment groups
- Rate and severity of Xenform exposure and erosion within 6, 12, 18, 24, 36 months
- Assessment of rate of adverse device or procedure related events in subjects with reoperation for failed prolapse repair
- Assessment of rates of/times to reoperation
- Comparison of rate of adverse device or procedure related events in subjects with re-surgery in both treatment groups
- Assessment and comparison between groups of analgesic intake and pain scoring at post-operative 6 weeks, 12, 18, 24, 36 months. Pain score improvement will be analyzed with a paired t-test for each group on all patients and with the propensity score adjusted confidence intervals for the pain score differences between groups. Change in analgesic intake from baseline will be analyzed by McNemar's test for each group on all patients.
- Assessment of severe blood loss during surgical procedure
- Duration of surgery from operative report
- Assessment of re-treatment interventions (i.e. surgery, office-procedure, etc.)
- Assessment of days to discharge and return to normal activity
- Assessment of risk factors, including menopausal status, estrogen use, age smoking, diagnosis of diabetes, body mass index, concomitant procedures, surgeon training and experience

A comparison of data between baseline and 36 months for all subjects will be included per the following statistical analyses to measure for secondary endpoints:

- Quality of Life Assessments (PFIQ, PFDI, PISQ, TOMUS) at 6, 12, 18, 24, 36 months as compared to baseline: paired t-test will be used to compare mean QOL score improvement from baseline to 6, 12, 18, 24 and 36 months for each group.
- Comparison of Quality of Life Assessments improvements between treatment groups
- Assessment of Quality of Life in subjects with re-surgery after re-surgery
- Assessment of subject satisfaction at 6, 12, 18, 24, 36 months (PGI-I for Prolapse)

Propensity score adjusted confidence intervals described in Section 12.2.3 (Propensity Score Methodology) will be used to evaluate continuous variables including QOL score improvements between two groups.

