			12.1.1.3. Statistical Methods; 12.2.1. Analysis Sets	Added “per protocol” group to primary safety endpoint evaluation	To clarify evaluation of the primary safety endpoint
			12.3.5.4. Subjects with surgical intervention for recurrence or complications	Added section	To specify the analysis of adverse events by vaginal compartment after re-surgery
09/AE	20 March 2018	90702637 Rev/Ver AH	11.1. Data Collection; 11.4.5. Follow-Up	Increased window for follow-up visits to occur	To reduce number of late visits
			11.4.5. Follow-Up	Provide option for completion of home or phone follow-up visits; revised start day for visit window calculation	To improve collection of follow-up visit data and correct error in calculation of visit windows
			12.1.1.3. Statistical Methods	Added tipping point analysis	To clarify the sensitivity analyses to be performed

Revision History

Revision Number	Release Date	Template Number and Version	Section	Change	Reason for Change
			12.2.3. Propensity Score Methodology	Added definition of treatment arms	To clarify how logistic regression will be performed
			12.3.8. Interim Analysis	Added details of interim analysis of 12 month outcomes	Requested by FDA

** Not released to the study sites.*

2. Protocol Synopsis

Postmarket Study PS120081: A Prospective, Non-Randomized, Parallel Cohort, Multi-Center Study of Xenform vs. Native Tissue for the Treatment of Women with Anterior/Apical Pelvic Organ Prolapse	
Study Objective(s)	The purpose of this study is to compare transvaginal repair with a biologic graft to traditional native tissue repair in women surgically treated for anterior and/or apical pelvic organ prolapse. This study is being conducted in partnership with the American Urogynecologic Society (AUGS) under the Pelvic Floor Disorders Outcome Registry (PFD Registry).
Test Device	Xenform Soft Tissue Repair Matrix biologic graft (“Xenform”)
Control Device	Traditional native repair (sacrospinous ligament fixation or uterosacral ligament suspension and/or colporrhaphy)

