11.4.5. Follow-Up

Subjects will be scheduled for follow-up visits as outlined in Table 11.1-1 (Data Collection Schedule). The follow-up visit schedule begins from the day of the study surgery and includes visit windows (counted in calendar days).

Every effort should be made to do the follow-up visit within the window; however, if this is not possible, the site should attempt to complete the visit as soon as possible but before the next visit window opens. Follow-up visits will be considered missed once the visit window for the next follow-up visit opens. For the Month 36 visit, the visit is not considered missed until the last day of the visit window (i.e., +12 weeks).

Every effort should be made to conduct the follow-up visit at the study site location. However, if the subject cannot physically return to the site for any reason, the follow-up visit may be conducted at the subject's home with their consent and if allowed by local institutional policy and the IRB/EC. If a home visit is not possible, every effort should be made to conduct as much of the visit as possible by phone (i.e., assess adverse events, risk factors, and analgesic intake) and to send the subject questionnaires by mail for completion.

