12.2. General Statistical Methods

12.2.1. Analysis Sets

The Intent-to-Treat (ITT) subject population includes all subjects who provide written informed consent to be enrolled into the study and have a surgery initiated (i.e. incision in vagina) regardless of their adherence with the entry criteria, regardless of treatment and withdrawal/protocol deviations.

The treated population includes all subjects who undergo a study surgical procedure. The subject is defined to have successfully completed the surgical procedure (i.e. prolapse repair successful) and discharged.

The Per Protocol (PP) population includes all subjects in the ITT Population who received the assigned treatment and had no major protocol deviations.

All primary and secondary endpoints will be analyzed on the ITT Population. The primary safety endpoint and non-safety endpoints will also be analyzed on the per-protocol population.

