19.2.1. Xenform Exposure and Erosion Event Classification

Assessment of Xenform exposure and/or erosion will occur at all follow-up visits with pelvic examinations performed at 2, 6, 12, 18, 24, and 36 Months post-procedure. Identification of Xenform exposure and/or erosion will occur by the medical staff member performing the pelvic exam and will be documented as an adverse event on the Case Report Forms.

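### Rates of exam-detected complications to Month 36 have no rule for women without a late pelvic exam, so late rates would be understated

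*Combined protocol and SAP*

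**What the plan says.** - **Detection.** Section 19.2.1: "Identification of Xenform exposure and/or erosion will occur by the medical staff member performing the pelvic exam". The finding is recorded as an adverse event. Exams are planned at Months 2, 6, 12, 18, 24 and 36, and vaginal length is measured at the same exam (Table 11.1-1).
- **Rates.** Section 12.1.2.3 lists "Rate and severity of Xenform exposure and erosion within 6, 12, 18, 24, 36 months" among analyses covering all subjects.
- **Analysis set.** Section 12.2.1: "All primary and secondary endpoints will be analyzed on the ITT Population".
- **Phone visits.** Revision 09/AE, dated 20 March 2018, changed Section 11.4.5: "Provide option for completion of home or phone follow-up visits". If neither a site nor a home visit can be held, the site should "conduct as much of the visit as possible by phone (i.e., assess adverse events, risk factors, and analgesic intake"), with questionnaires sent by mail. A phone visit includes no pelvic exam.
- **Missing data.** The imputation and sensitivity methods in Sections 12.1.1.3 and 12.3.8.2 cover only the composite effectiveness endpoint. Section 12.1.1.3 writes out an all-subjects denominator for the primary safety endpoint alone. Section 12.3 gives a general rule that summaries use non-missing data.
- **Compared adverse events.** Vaginal shortening and vaginal scarring belong to the composite in Sections 12.1.2.1 and 12.1.2.2, which assume a rate of 12%, a margin of 8.9% and 165 women per arm.

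**The concern.** A silent exposure or a shortened vagina can be found only if someone looks. If a woman's last exam was at Month 18 or 24, her status for these events is unknown after that date. A cumulative proportion over the whole ITT set treats unknown as absent.

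Three routes lead there: loss to follow-up, a missed visit, and a phone-only visit. The third is the hardest to see in the data. Under Section 10.2.3 a woman must be unreachable and have missed two consecutive visits before she may be called lost. A woman reached by phone stays in follow-up with an adverse-event assessment on record, so the usual remedy of censoring at last contact leaves her in the risk set.

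Exposure and erosion are named secondary safety endpoints of a post-market device study. At stake is whether a flat curve between Months 24 and 36 reflects few events or few exams. For the compared composite, under-detection narrows the observed difference and so favors non-inferiority.

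**Working it through.** **1. When the phone option can apply.** Enrollment ran from February 2014 to December 2016 (Table 10.1-1) and is counted from the incision (Section 10.1), so it dates surgery. Take 1 February 2014 to 31 December 2016, which is 1,064 days, and assume uniform enrollment. A target visit falls on or after 20 March 2018 if surgery was on or after:

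- Month 18: 20 September 2016; 102/1,064 = 9.6%
- Month 24: 20 March 2016; 286/1,064 = 26.9%
- Month 36: 20 March 2015; 652/1,064 = 61.3%

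No Month 2 or 6 visit and no Month 12 target date qualifies; only a Month 12 visit at the very end of its window or later could. These are shares of visits *eligible* for the option, not phone visits.

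**2. The plan's own figure.** Composite, 12% per arm, margin 8.9%, one-sided 5%, 80% power:

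n = (1.645 + 0.842)² × 2 × 0.12 × 0.88 / 0.089² = 164.8, so 165 per arm, as stated. No expected rate, margin or sample size is given for exposure or erosion.

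**3. Single-arm rates.** Let f be the share of women with no late exam, L the share of events arising after their last exam, and q the share of events that only an exam finds. If unexamined women count as event-free:

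observed rate = true rate × (1 − f × q × L)

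The documents give none of these inputs directly. As an illustration, set f = 20% (borrowing the planned loss to follow-up) and q = 1 as an upper bound. With L = 1/3 the cumulative rate is low by 0.20 × 1/3 = 6.7% of its value; with L = 1/4, by 5.0%. The late increment itself is low by the full 20%, which is why the end of the curve is the part most affected.

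**4. Composite at the margin.** True rates are 20.9% and 12%. With p_T = 0.209(1 − f_T q L) and p_C = 0.12(1 − f_C q L), and the 90% confidence interval rule:

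false non-inferiority rate = Φ[(0.089 − (p_T − p_C))/SE − 1.645], SE² = p_T(1 − p_T)/165 + p_C(1 − p_C)/165

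Example (f_T = 20%, f_C = 5%, q = 40%, L = 1/3): p_T = 0.2034, p_C = 0.1192, difference 0.0842, SE 0.0402. This gives Φ(0.119 − 1.645) = 6.35%.

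| L | No late exam, Xenform / control | q = 20% | q = 40% |
|---|---|---|---|
| 1 | 20% / 5% | 7.13% | 9.97% |
| 1 | 10% / 10% | 5.47% | 5.99% |
| 1/3 | 20% / 5% | 5.64% | 6.35% |
| 1/3 | 10% / 10% | 5.15% | 5.31% |
| 1/4 | 20% / 5% | 5.47% | 5.99% |
| 1/4 | 10% / 10% | 5.11% | 5.23% |

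The nominal value is 5.0%. With 227 per arm, the full planned ITT set, the 20% / 5% rows become 5.8 to 6.6% (L = 1/3) and 5.6 to 6.2% (L = 1/4). The rows with L = 1 treat these women as never examined, which contradicts their exams up to the last one.

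**The case against.** **A reader might infer that the 2018 amendment caused complications to be looked for less often.** The documents do not support this. Phone contact is the third choice: "If a home visit is not possible, every effort should be made to conduct as much of the visit as possible by phone". The likely alternative was a missed visit, which also has no exam. The stated reason was "To improve collection of follow-up visit data and correct error in calculation of visit windows", and the same revision added home visits and widened windows, both of which may increase exams. This objection stands: phone visits are one route into a general gap, and the planned 20% loss may be the larger one.

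**A reader might infer that the plan states that unexamined women count as event-free.** It does not. Section 12.2.1 names an analysis set, not a denominator at each time point, and the non-missing rule in Section 12.3 leaves room for another reading. This stands as a point about wording. It does not close the gap, because exposure is an adverse-event record. No record is not a missing value, and a phone visit that asks about adverse events plausibly yields a plain negative.

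**A reader might infer a false non-inferiority rate of 7 to 10%, or a bias by arm.** The first needs L = 1. The second is possible, since centers are one-arm by default (Section 12.2.2), but nothing in the documents shows it. Exposure and erosion have no hypothesis or margin and are not in the composite. Most composite components, such as pelvic pain, discharge and bleeding, can be reported by phone. Symptomatic exposure can also surface between visits; Section 11.5 mentions office trimming.

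**Conclusion.** The concern holds as a gap in how exam-detected events are estimated. Detection depends on the exam, the rates are cumulative on ITT, the only denominator written out is all subjects, and no missing-data rule reaches these rates. As naturally read, the plan understates late rates.

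For exposure and erosion the result is a single-arm rate that is too low. Under the illustrative inputs this is 5 to 7% of the cumulative rate and up to 20% of the late increment. For the composite the effect is confined to components such as vaginal shortening and scarring and is probably small: false non-inferiority of about 5.1 to 6.4% with 165 per arm, or up to 6.6% with 227, against 5%.

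These sizes rest on assumed shares of women without a late exam, of late events and of exam-only events. The timing shares rest on uniform enrollment. The number of phone visits and their split by arm are not given.

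**What to change.** 1. In Section 12.1.2.3, estimate cumulative rates of exam-detected events (exposure, erosion, vaginal shortening, vaginal scarring) by Kaplan-Meier or, preferably, interval-censored methods. Event-free time ends at the last pelvic exam. Events reported later by phone or at an unscheduled visit still count.
2. Report by arm and visit the number of women examined.
3. For the composite, add a sensitivity analysis that applies the same censoring to its exam-detected components, or that imputes status for unexamined women. Do not restrict to women with a Month 36 exam or an earlier event: that keeps every early case, drops event-free women without an exam, and biases rates upward.

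The cost is analysis wording and a few tables, with no added visits or exams. The downside is slightly fewer women at risk and slightly wider late intervals. Counting late-reported events without matching event-free time also pulls the estimate up a little, so the number of such events should be shown.
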